11.0 Treatment Evaluation

Revised International Working Group for Myeloproliferative Neoplasms Research and Treatment (IWG-MRT) as defined by IWG-MRT criteria (Tefferi et al. Blood. 2013)

Table 11.1

Response categories	Required criteria
Complete Remission (CR)	
Bone marrow:* Age-adjusted normocellularity; <5% blasts; \leqGrade 1 myelofibrosis**, AND
 
Peripheral blood: Hemoglobin \geq100 g/L and <UNL; Neutrophil count \geq1 \times 10⁹/L and <UNL;
 
Platelet count \geq100 \times 10⁹/L and <UNL; <2% immature myeloid cells***, AND
 
Clinical: Resolution of disease symptoms; Spleen and liver not palpable; No evidence of EMH

Partial Remission (PR)	
Peripheral blood: Hemoglobin \geq100 g/L and <UNL; Neutrophil count \geq1 \times 10⁹/L and <UNL;
 
Platelet count \geq100 \times 10⁹/L and <UNL; <2% immature myeloid cells***, AND
 
Clinical: Resolution of disease symptoms; Spleen and liver not palpable; No evidence of EMH
 
OR
 
Bone marrow:* Age-adjusted normocellularity; <5% blasts; \leqGrade 1 myelofibrosis**, AND
 
Peripheral blood: Hemoglobin \geq85 but <100 g/L and <UNL; Neutrophil count \geq1 \times 10⁹/L and <UNL;
 
Platelet count \geq50 but <100 \times 10⁹/L and <UNL; <2% immature myeloid cells***, AND
 
Clinical: Resolution of disease symptoms; Spleen and liver not palpable; No evidence of EMH

Clinical improvement (CI)	
The achievement of anemia, spleen or symptoms response without progressive disease or
 
increase in severity of anemia, thrombocytopenia or neutropenia‡

Anemia response	
Transfusion-independent patients: a \geq20 g/L increase in hemoglobin level†
 
Transfusion-dependent patients: becoming transfusion-independent††

Spleen Response §	
A baseline splenomegaly that is palpable at 5-10 cm, below the LCM, becomes not palpable§§, OR
 
A baseline splenomegaly that is palpable at >10 cm, below the LCM, decreases by \geq50%§§
 
A baseline splenomegaly that is palpable at <5 cm, below the LCM, is not eligible for spleen response
 
A spleen response requires confirmation by MRI or CT showing \geq35% spleen volume reduction (optional)

Symptoms response	
A \geq50% reduction in the Myeloproliferative Neoplasm Symptom Assessment Form total symptom score (MPN-SAF TSS)

Progressive Disease ¶ (PD)	
Appearance of a new splenomegaly that is palpable at least 5 cm below the LCM, OR
 
A \geq100% increase in palpable distance, below LCM, for baseline splenomegaly of 5 to 10 cm, OR
 
A 50% increase in palpable distance, below LCM, for baseline splenomegaly of >10 cm, OR
 
Leukemic transformation confirmed by a bone marrow blast count of \geq20%, OR
 
A peripheral blood blast content of \geq20% associated with an absolute blast count of \geq1 \times 10(9)/L that lasts for at least two weeks

Stable Disease (SD)	Belonging to none of the above listed response categories
Relapse (REL)	No longer meeting criteria for at least CI after achieving CR, PR or CI, OR Loss of anemia response persisting for at least one month, OR Loss of spleen response persisting for at least one month

Key: UNL, upper normal limit; LCM, left costal margin; MRI, magnetic resonance imaging; CT, computed tomography; EMH, extramedullary hematopoiesis (no evidence of EMH implies the absence of pathology- or imaging study-proven non-hepatosplenic EMH) ;

*Baseline and post-treatment bone marrow slides are to be stained at the same time and interpreted at one sitting by a central review process. Cytogenetic and molecular responses are not required for CR assignment.

**Grading of myelofibrosis is according to the European classification (*Thiele et al. Haematologica 2005;90:1128*) . It is underscored that the consensus definition of “a complete remission bone marrow” is to be used only in those patients where all other criteria, including resolution of leukoerythroblastosis, are met. It should also be noted that it was a particularly difficult task for the working group to reach a consensus regarding what represents a complete histological remission.

***Immature myeloid cells constitute blasts + promyelocytes + myelocytes + metamyelocytes + nucleated red blood cells. In splenectomized patients, <5% immature myeloid cells is allowed.

See table 11.1 for definitions of anemia response, spleen response and progressive disease. Increase in severity of anemia constitutes the occurrence of new transfusion dependency or a ≥ 20 g/L decrease in hemoglobin level from pre-treatment baseline that lasts for at least 12 weeks. Increase in severity of thrombocytopenia or neutropenia is defined as a 2-grade decline, from pre-treatment baseline, in platelet count or absolute neutrophil count, according to Common Terminology Criteria for Adverse Events (CTCAE) version 4.0. In addition, assignment to clinical improvement (CI) requires a minimum platelet count of $\geq 25,000 \times 10(9)/L$ and absolute neutrophil count of $\geq 0.5 \times 10(9)/L$

Applicable only to patients with baseline hemoglobin of <100 g/L. In patients not meeting the strict criteria for transfusion-dependency at the time of study enrollment (see below), but have received transfusions within the previous month, the pre-transfusion hemoglobin level should be used as the baseline

Transfusion dependency before study enrollment is defined as transfusions of at least 6 units of packed red blood cells (PRBC), in the 12 weeks prior to study enrollment, for a hemoglobin level of <85 g/L, in the absence of bleeding or treatment-induced anemia. In addition, the most recent transfusion episode must have occurred in the 28 days prior to study enrollment. Response in transfusion dependent patients requires absence of any PRBC transfusions during any consecutive “rolling” 12-week interval during the treatment phase, capped by a hemoglobin level of ≥ 85 g/L.

In splenectomized patients, palpable hepatomegaly is substituted with the same measurement strategy

Optional, Spleen or liver responses can be confirmed by imaging studies where a $\geq 35\%$ reduction in spleen volume, assessed by magnetic resonance imaging (MRI) or computed tomography (CT), is required. Furthermore, a $\geq 35\%$ volume reduction in the spleen or liver, by MRI or CT, constitutes a response regardless of what is reported with physical examination.

Symptoms are evaluated by the Myeloproliferative Neoplasm Symptom Assessment Form total symptom score (MPN-SAF TSS).¹⁷ The MPN-SAF TSS is assessed by the patients themselves and includes fatigue, concentration, early satiety, inactivity, night sweats, itching, bone pain, abdominal discomfort, weight loss, and fevers. Scoring is from 0 (absent/as good as it can be) to 10 (worst imaginable/as bad as it can be) for each item. The MPN-SAF TSS is the summation of all the individual scores (0-to-100 scale). Symptoms response requires $\geq 50\%$ reduction in the MPN-SAF TSS.

Optional, Progressive disease assignment for splenomegaly requires confirmation my MRI or CT showing a $\geq 25\%$ increase in spleen volume from baseline. Baseline values for both physical examination and imaging studies refer to pre-treatment baseline and not to post-treatment measurements.

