9.0 Ancillary Treatment/Supportive Care

- 9.1 Antiemetics may be used at the discretion of the attending physician.
- 9.2 Blood products and growth factors should be utilized as clinically warranted and following institutional policies and recommendations. The use of growth factors should follow published guidelines of the American Society of Clinical Oncology (42) Update of Recommendations for the Use of Hematopoietic Colony-Stimulating Factors: Evidence-Based, Clinical Practice Guidelines. J Clin Oncol 18(20): 3558-3585, 2000.
- 9.3 Patients should receive full supportive care while on this study. This includes blood product support, antibiotic treatment, and treatment of other newly diagnosed or concurrent medical conditions. All blood products and concomitant medications such as antidiarrheals, analgesics, and/or antiemetics received from the first day of study treatment administration until 30 days after the final dose will be recorded in the medical records.

9.4 Diarrhea: This could be managed conservatively with loperamide. The recommended dose of loperamide is 4 mg at first onset, followed by 2 mg every 2-4 hours until diarrhea free (maximum 16 mg/day).

In the event of grade 3 or 4 diarrhea, the following supportive measures are allowed: hydration, octreotide, and antidiarrheals.

If diarrhea is severe (requiring intravenous rehydration) and/or associated with fever or severe neutropenia (grade 3 or 4), broad-spectrum antibiotics must be prescribed.

Patients with severe diarrhea or any diarrhea associated with severe nausea or vomiting **should be hospitalized** for intravenous hydration and correction of electrolyte imbalances.

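### For patients not transfusion-dependent at baseline, the 20 g/L anemia-response rule sets no transfusion-free condition on the on-study hemoglobin, so a transfused value can count as a primary success

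*Combined protocol and SAP*

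**What the plan says.** Table 11.1 in Section 11.0 splits anemia response by transfusion status. Patients who are not transfusion-dependent need "a \geq20 g/L increase in hemoglobin level". The footnotes add two things to this branch:

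- "Applicable only to patients with baseline hemoglobin of <100 g/L".
- For a patient who was transfused in the month before enrollment but misses the strict dependency definition, "the pre-transfusion hemoglobin level should be used as the baseline".

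For the other branch, "Response in transfusion dependent patients requires absence of any PRBC transfusions during any consecutive" rolling 12-week interval on treatment, ending with a hemoglobin of at least 85 g/L.

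An anemia response alone is enough for CI, provided there is no progression and no worsening of anemia, thrombocytopenia or neutropenia. On anemia, "Increase in severity of anemia constitutes the occurrence of new transfusion dependency", or a fall of at least 20 g/L from baseline lasting at least 12 weeks. The only numerical definition of dependency refers to the time before entry: "Transfusion dependency before study enrollment is defined as transfusions of at least 6 units of packed red blood cells (PRBC") in 12 weeks, given for hemoglobin below 85 g/L, with bleeding and treatment-induced anemia excluded.

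Transfusion is allowed on study. Section 9.2 states "Blood products and growth factors should be utilized as clinically warranted", and 9.3 says of full supportive care "This includes blood product support". Section 16.11 makes a best response of CR, PR or CI, over all treatment cycles, a primary success.

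**The concern.** Section 11.0 recognises that transfusion distorts hemoglobin in two places: the baseline value of recently transfused patients, and the response of dependent patients. It is silent in the third place, the on-study value of patients who are not dependent. There a reading taken after a transfusion may be compared with a baseline taken before one, and the difference may reflect donor red cells and not P1101. With no stated duration, a single reading suffices, and a later loss of response does not undo a best response.

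The situation is not remote for this trial. Hemoglobin below 10 g/dL is by itself a qualifying criterion (3.10), it carries two DIPSS points (Appendix VI), and anemia is among the events listed for repeated P1101 dosing (15.17). At stake is the success count in Cohort 2, where the Stage 1 rule in 16.211 turns on 0, 1 to 3, or at least 4 successes in 12 patients.

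**Working it through.** **1. Does any rule reach the on-study value?**

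| Rule in Section 11.0 | Applies to | Covers an on-study transfused value in the 20 g/L branch? |
|---|---|---|
| Pre-transfusion hemoglobin | Baseline of patients transfused in the previous month | No |
| Rolling 12 weeks without red cells | Patients dependent at baseline | No |
| New transfusion dependency blocks CI | All patients, but dependency is defined only before enrollment | In part |
| Fall of at least 20 g/L for at least 12 weeks blocks CI | All patients | In part; it does not catch a patient whose hemoglobin transfusion keeps up |

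If the pre-enrollment threshold is used on study (an assumption), up to 5 units in 12 weeks do not trigger the third rule.

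**2. The plan's own figures (16.24).** Let X1 be the successes among 12 and X2 those among the next 23, both binomial with success probability p.

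- Stop for no successes: (1 − p)^12. At p = 0.10 this is 0.9^12 = 0.282 (plan 0.28).
- P(declare) = P(X1 ≥ 4) + Σ over x = 1, 2, 3 of P(X1 = x) × P(X2 ≥ 7 − x).
- At p = 0.10: 0.0256 + 0.3766 × 0.0226 + 0.2301 × 0.0731 + 0.0852 × 0.1927 = 0.0256 + 0.0085 + 0.0168 + 0.0164 = 0.067 (plan 0.07).
- At p = 0.30 the same formula gives 0.931 (plan 0.93).

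The table reproduces; no stated figure is in dispute.

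**3. One miscounted success among the first 12, with the other 11 responding at 10%.**

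- P(0 of 12) = 0, necessarily, against 0.282.
- P(at least 4 of 12) = P(Bin(11, 0.10) ≥ 3) = 1 − (0.3138 + 0.3835 + 0.2131) = 0.090, against 0.026.

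**4. Range for an assumed miscount rate.** Let q be the chance that a true non-responder is scored CI through a transfusion. Then p = 0.10 + 0.90q. The documents give no value for q.

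| q (assumed) | p | P(0 of 12) | P(at least 4 of 12) |
|---|---|---|---|
| 0 | 0.100 | 0.282 | 0.026 |
| 2% | 0.118 | 0.222 | 0.044 |
| 5% | 0.145 | 0.153 | 0.083 |

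q is an average over all non-responders. Only those with baseline hemoglobin below 100 g/L, not dependent, and transfused on study can contribute, so the rate among exposed patients would have to be higher than q.

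**5. What a 12-week condition would cost.** Cycles are 28 days (Section 4.0).

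- The C6 evaluation falls on day 5 × 28 = 140, week 20. A transfusion after week 20 − 12 = 8 rules it out.
- The last scheduled CBC before 6 months is C7 Day 1, day 6 × 28 = 168, week 24 (C8 Day 1 is week 28). A transfusion after week 24 − 12 = 12 rules it out.
- Power at a true 30%, if a share of true successes were lost (assumed shares): 5% lost gives p = 0.285 and power 0.90; 10% lost gives p = 0.27 and power 0.87, against 0.93.

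**The case against.** The strongest reply is that Section 11.0 restates a published consensus, which may itself contain a transfusion or duration condition. That cannot be settled from the documents, so a reader who infers that the consensus criteria are deficient goes too far. What is established is that the protocol's text lacks the condition, and 16.11 points to Section 11.0 for the detail.

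Next, the branch is labelled as being for transfusion-independent patients, and transfusion is assessed at the same visits as response. This makes it less likely that a careful investigator would score a transfused value. It does not close the gap: the footnote places recently transfused patients in this branch if they miss the strict definition, so the label describes baseline status and is not a condition at response.

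Third, the guards have force. If P1101 lowers hemoglobin, transfusion must make good that fall and then add 20 g/L above baseline, and a long enough fall blocks CI altogether. Nor can units spread over 12 weeks be assumed to add up fully at one blood count. Both points limit the frequency; neither makes the event impossible.

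A reader might also infer from the assumed miscount rates that the design's false-positive rate is inflated by a known amount. The documents do not support that: they give no such rate, and the 10% null may already allow for some background response. Nor does a miscount force a wrong decision. With 1 to 3 successes an amendment is only considered, with 4 or more further testing may be recommended, and 16.25 brings quality and duration of response into decisions to terminate.

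**Conclusion.** The gap is real and lies in the definition of the primary endpoint. For patients with baseline hemoglobin below 100 g/L who are not transfusion-dependent, Section 11.0 as written lets a hemoglobin raised by transfusion count as CI and as a primary success. The two guards within CI reduce this without removing it.

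The frequency is unknown and the exposed subgroup is limited. The size is best read as sensitivity: in a 12-patient rule, a single miscount is enough to remove the futility stop and to raise the chance of meeting the positive threshold about 3.5-fold (0.090 / 0.026), assuming a true rate of 10% in the other 11. That merits a clarification before responses are adjudicated. It does not invalidate the design or its operating characteristics.

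**What to change.** For endpoint scoring only, with no bearing on when patients are transfused:

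- In Section 11.0, count the rise of at least 20 g/L only on hemoglobin values with no red-cell transfusion in the preceding 12 weeks, the window already used for dependent patients. Derive this from the transfusion assessment (4.0), the Concurrent Transfusion form (18.1) and the diary (Appendix V).
- If new transfusion dependency is given an on-study definition for scoring CI, do not carry over the pre-enrollment exclusion of treatment-induced anemia. Otherwise transfusions for P1101-related anemia would not count, and the guard would be weakened.
- Leave the decision rule and the 10% and 30% rates unchanged.

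The cost is wording and derivation, with no new data. Some true rises will be recognised later: after a transfusion beyond about week 8 a rise cannot count at the C6 evaluation, and beyond about week 12 it cannot count on any scheduled CBC before 6 months. It can still count afterwards, because best response runs over all cycles. If some true successes are lost altogether, power falls modestly, as shown in the working.

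A descriptive summary of how long spleen and symptom responses last would be a separate, optional addition.

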3.14 No prior treatment for myelofibrosis (for Cohort 1 only)

3.15 ECOG Performance Status (PS) 0, 1 or 2 (Appendix I).

3.16 The following laboratory values obtained \leq 14 days prior to registration.

- Platelet count \geq 100,000/mm³
- Absolute Neutrophil Count (ANC) \geq 1000/mm³
- Aspartate transaminase (AST) \leq 2.5 x ULN
- Alanine aminotransferase (ALT) \leq 2.5 x ULN
- Calculated creatinine clearance must be \geq 50 ml/min using the Cockcroft-Gault formula below:

Cockcroft-Gault Equation:

$$\text{Creatinine clearance for males} = \frac{(140 - \text{age})(\text{weight in kg})}{(72)(\text{serum creatinine in mg/dL})}$$

$$\text{Creatinine clearance for females} = \frac{(140 - \text{age})(\text{weight in kg})(0.85)}{(72)(\text{serum creatinine in mg/dL})}$$

- 3.17 Negative pregnancy test done \leq 7 days prior to registration, for women of childbearing potential only.
- 3.18 Ability to complete questionnaire(s) by themselves or with assistance.
- 3.19a Provide informed written consent.
- 3.19b Willing to return to enrolling institution for follow-up per section 4.0
- 3.19c Willing to provide blood samples for correlative research purposes (see Sections 6.2 and 14.0)

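### The platelet floor for Clinical Improvement is printed as 25,000 x 10^9/L, 250 times the entry and complete-remission floors: a probable unit slip in the primary-endpoint criteria

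*Combined protocol and SAP*

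**What the plan says.** Section 16.11 counts a patient as a success if the best overall response is CR, PR or CI, and points to Section 11.0 for the criteria. In Section 11.0, the footnote that qualifies CI sets two absolute blood-count minima. For platelets: "assignment to clinical improvement (CI) requires a minimum platelet count of $\geq 25,000 \times 10(9)/L". For neutrophils, in the same sentence: "absolute neutrophil count of $\geq 0.5 \times 10(9)/L". The sentence before gives a relative rule, under which worsening thrombocytopenia or neutropenia, which rules out CI, is "defined as a 2-grade decline, from pre-treatment baseline, in platelet count or absolute neutrophil count".

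The other platelet limits in the protocol are:

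- Entry (Section 3.16): "Platelet count \geq 100,000/mm³"
- CR, and the first PR route (Table 11.1): "Platelet count \geq100 \times 10⁹/L and <UNL"
- Second PR route (Table 11.1): "Platelet count \geq50 but <100 \times 10⁹/L and <UNL"

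The progressive-disease row of Table 11.1 uses the same unit notation as the footnote, with a value on the usual scale: "absolute blast count of \geq1 \times 10(9)/L that lasts for at least two weeks".

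**The concern.** CI is the lowest response tier: Table 11.1 defines relapse as no longer reaching at least CI after CR, PR or CI. A platelet minimum for the lowest tier that is far above the minimum for complete remission contradicts that ordering, and the second PR route even requires platelets below 100 x 10^9/L.

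The footnote is part of the endpoint definition. If it were applied as printed, nobody could be scored CI. Only CR and PR would then count towards the cohort 2 rules in Sections 16.211 and 16.212 (0 of 12, 4 or more of 12, 7 or more of 35), and the relapse definition would be affected too. If it is not applied as printed, each assessor has to substitute a threshold that the protocol does not give. In a 12-patient first stage, one reclassified patient can move the count from 0 to 1 or from 3 to 4.

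**Working it through.** **Conversion.** 1 L = 10^6 mm³.

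- CI floor as printed: 25,000 x 10^9/L = 2.5 x 10^13/L; divided by 10^6, this is 25,000,000/mm³.
- Entry floor (Section 3.16): 100,000/mm³ x 10^6 = 10^11/L = 100 x 10^9/L.

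**Ratios, all in units of 10^9/L.**

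| Comparator | Value | CI floor ÷ comparator |
|---|---|---|
| Entry floor | 100 | 25,000 / 100 = 250 |
| CR floor (also first PR route) | 100 | 25,000 / 100 = 250 |
| Lower PR floor (second route) | 50 | 25,000 / 50 = 500 |
| 25,000/mm³ (inferred intention) | 25 | 25,000 / 25 = 1,000 |

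**All per-litre lower limits for cell counts in Section 11.0 (10^9/L).**

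| Criterion | Neutrophils | Platelets | Blasts |
|---|---|---|---|
| CR | 1 | 100 | |
| PR, first route | 1 | 100 | |
| PR, second route | 1 | 50 | |
| Progressive disease | | | 1 |
| CI | 0.5 | **25,000** | |

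There are nine limits. Eight lie between 0.5 and 100, and only the CI platelet floor does not.

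**Which part is off.** The CI neutrophil floor is 0.5 x 10^9/L against an entry floor of 1,000/mm³ = 1 x 10^9/L, a ratio of 0.5. The per-litre unit therefore works for the other half of the same sentence. If 25,000 was meant per mm³, the scale of the entry criterion, the platelet floor becomes 25 x 10^9/L. That is 25/100 = 0.25 of the entry and CR floors and 25/50 = 0.5 of the lower PR floor, which fits the ordering of the tiers.

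**Effect on the design figures.** With X1 ~ Bin(12, p) and X2 ~ Bin(23, p):

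P(declare worthwhile) = P(X1 ≥ 4) + Σ(x = 1 to 3) P(X1 = x) · P(X2 ≥ 7 − x)

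| True p | 0.10 | 0.15 | 0.20 | 0.25 | 0.30 | 0.35 |
|---|---|---|---|---|---|---|
| Recomputed | 0.067 | 0.282 | 0.576 | 0.808 | 0.931 | 0.980 |
| Section 16.24 | 0.07 | 0.28 | 0.58 | 0.81 | 0.93 | 0.98 |

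The stage 1 futility probability at p = 0.10 is 0.9^12 = 0.282 (stated 0.28). The table reproduces and does not depend on the CI floor.

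**Outer bound under literal use (illustration only).** The protocol gives no split of expected responses, so the CI-only share is an assumption. Take a true success rate of 30%. If half of successes were CI only, the countable rate would be 0.30 x 1/2 = 15%, and the chance of a positive conclusion would fall from 0.93 to 0.28. If two thirds were CI only, the countable rate would be 0.30 x 1/3 = 10%, and the chance would be 0.07.

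**The case against.** The strongest reply is that this is a typographical slip too large to mislead. It sits beside CR and PR floors that show it to be impossible, and Sections 2.11 and 11.0 name the IWG-MRT criteria, so an assessor has somewhere to look. Patients enter with at least 100 x 10^9/L platelets, and the 2-grade decline rule already bars CI after a marked fall. It is therefore unclear how often a corrected absolute floor would matter. CTCAE cut-offs are not in the protocol, so that frequency cannot be computed. The replacement value is also not in the protocol, and if the footnote was copied, the oddity could be in the source itself.

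Most of this stands. It limits the weight of the point: literal use is unlikely, no effect on conduct has been shown, and the illustrative losses of power should not be read as expected. It does not remove the error. Section 16.11 sends the reader to Section 11.0 for the endpoint, so the printed text governs until corrected. A reading fault in the electronic text is also unlikely, because the thousands separator is present and the same unit notation reads normally elsewhere in Section 11.0.

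**Conclusion.** The concern holds, as a minor point. The printed CI platelet floor is 250 times the entry and CR floors and 500 times the lower PR floor. It is also the only one of nine comparable limits outside 0.5 to 100. These statements need no assumption.

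Two things are inferred: that a per-mm³ number was paired with a per-litre unit, and hence that the intended floor is 25 x 10^9/L and the printed one 1,000 times too high. Misclassification follows only if the footnote is applied literally. Confidence is high that the figure is wrong, and lower as to its replacement.

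**What to change.** Before responses are scored, amend this one figure so that it is on the same scale as Table 11.1. The unit-consistent reading is at least 25 x 10^9/L (25,000/mm³), to be confirmed against the cited IWG-MRT criteria.

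Check the unit as well as the wording when confirming. The footnotes look carried over from another text: the symptom footnote keeps a reference number 17 ("MPN-SAF TSS).¹⁷ The MPN-SAF TSS is assessed by the patients themselves"), while the list in Section 20.0 ends at 8. That says nothing about the platelet unit itself, but it means the slip may have been inherited. If the source shows the same figure, record that and state the value adopted and the reason for it.

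Leave the 2-grade decline rule as it is, and use the same floor wherever response is scored.

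The cost is one number in one footnote, made by amendment because it defines the primary endpoint. It needs no extra patients, visits or data, and the decision rules do not change.
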